Aim 1a. and 1b. The outcome measures involved in this aim (e.g., parenting self-efficacy measured using the PMP S-E and perceived stress scale), are derived from multi-item scales and will be treated as continuous measurements. For each scale, the mean score after baseline will be assessed at each of the visits (1 week, 1 month, 3 months, 6 months and 12 months). The overall mean difference from baseline for each of the scales between the two intervention groups will be used to evaluate Aim 1. We will assess the overall change in scores for the self-efficacy and depression scales, i.e. the population averaged effect of the intervention on changes in self-efficacy and depression, using a generalized estimating equation (GEE) model to account for the correlation between the repeated change measurements among primary care givers. The GEE model is reasonably robust to missing data. We will use an exchangeable correlation structure, but in sensitivity analyses, will also test unstructured correlation and compare parameter estimates. The main independent variable in these analyses is intervention group, however we will also include (if necessary) a cross-product term of group-by-time which will enable us to estimate differences between the intervention groups over time. The group-by-time term will be included only if it is statistically significant. The model will include covariates reflecting the randomization stratification variables, and other covariates only if imbalances are observed in the randomization groups at baseline. In addition, we will use the model to plot the change in parental self-efficacy or parenting stress over time-by-group with 95% CI around each time point estimate. The degree of change at 3-months will allow us to assess the rapidity of any effect of intervention and a descriptive comparison of the differences between the groups at 6- and 12-months will allow us to assess the degree of persistence of any effect. We will consider the difference between groups to be statistically significant when the 95% confidence intervals around the difference do not include 0.

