Aim 2a. and 2.b. will compare measures of anxiety using the STAI, and depression using the CES-D in primary caregivers from the intervention and control groups. The independent variable will be the intervention group in both models. If necessary, the models will include covariates known to impact parental depression and anxiety (if different between the groups) and stratification variables. We will estimate and compare the covariate adjusted mean difference in the scores between the intervention

groups using GEE models as described above (Aim 1). The difference will be considered to be statistically significant if the 95% CI around the difference fails to include 0.

As in Aim 1, group-by time-interaction models will be used to evaluate differences between the groups over time.

Aim 3. The NICU graduates may experience multiple ED visits or hospitalizations any time after baseline. The number of ED or hospitalization counts will be summed for each of the intervention groups. To assess differences between the intervention groups for each of the outcomes (ED visits or hospitalizations), we will use the Wilcoxon–Mann–Whitney two-sample rank-sum test, which is appropriate for use with nonparametric data, such as the count data from this aim. We will define the outcome, improved immunization status, as receipt of two diphtheria-tetanus-acellular pertussis (DTaP) vaccines, two Hemophilus influenzae b (HIB) vaccines, and two pneumococcal conjugate vaccines (PCV-13) by the end of the observation period (12 months after baseline). This binary outcome will be contrasted using an unpaired t-test with unequal variances to measure the hypothesis that the intervention results in improved immunization status.

Sensitivity Analyses. In sensitivity analyses, we will explore the effect of departures from assumptions made for the main analysis. A key assumption in our analyses is that missing data are missing at random, and groups who are and are not lost to follow-up are similar. We will compare characteristics of families who are, and are not, lost to follow-up. If significant differences between these two ( $p < 0.05$ ) are observed, we can test for intervention effects, but with the assumption that individuals with missing data have worse outcomes. We will then report these ‘worst case’ scenarios and report any changes in the clinical interpretation of the trial.

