Sample Size & Power. We calculated power to detect projected differences between the intervention groups for the 3 primary outcomes. All computations are based on a projected sample size of 300 families of NICU infants (i.e. 300 primary care giver evaluations, and 300 NICU infant outcome evaluations) with randomization into 2 equal groups of 150, with data collected over multiple time points during the 12 months of follow-up post discharge. In Aims 1 and 2, we will have up to 5 repeated measures after baseline (1-week, 1-month, 3-months, 6-months, and 12-months), which increases our statistical power for those aims. We assumed a modest within-subject correlation of 0.50 between these repeated measures. Using Bonferroni correction, we adjusted alpha (0.05) for the number of primary outcomes,  $n=3$ . For Aim 1, we estimate that we will have excellent power (93%) to detect differences in parental self-efficacy scores as small as 0.33SD. This estimate is based on PMSPE score distributions as reported in the literature. For the main infant outcome of number of hospitalizations during the 12-month follow-up post discharge period, we estimate that we have excellent power (99%) to detect a difference of 1 in the median number of hospitalizations between the groups. Given our conservative assumptions, including modest correlation ( $r=0.5$ ) between repeated measures and Bonferroni correction for the number of primary outcomes, we believe that our sample size ensures sufficient power to measure clinically relevant differences between the intervention groups.

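### The sample size assumes a Bonferroni level of 0.05/3 for three primary outcomes, but Aims 1 and 2 are judged on unadjusted 95% intervals, Aim 3 has no level, and the three outcomes are never listed

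*SAP*

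**What the plan says.** The protocol and the SAP carry the same statistical text, so each point below applies to both.

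- **Sample Size & Power.** The paragraph opens with "We calculated power to detect projected differences between the intervention groups for the 3 primary outcomes" and continues "Using Bonferroni correction, we adjusted alpha (0.05) for the number of primary outcomes", with the number given as three. It later counts this correction among its conservative assumptions. It gives power for two outcomes. For self-efficacy, "we estimate that we will have excellent power (93%) to detect differences in parental self-efficacy scores as small as 0.33SD". The second is introduced with "For the main infant outcome of number of hospitalizations during the 12-month follow-up post discharge period". There is no power figure for a third.
- **Aim 1 (self-efficacy, stress).** The measure is change from baseline: "The overall mean difference from baseline for each of the scales between the two intervention groups will be used to evaluate Aim 1". The criterion is "We will consider the difference between groups to be statistically significant when the 95% confidence intervals around the difference do not include 0".
- **Aim 2 (anxiety, depression).** "The difference will be considered to be statistically significant if the 95% CI around the difference fails to include 0".
- **Aim 3.** A rank-sum test is named for ED visits and hospitalizations, and an unequal-variance t-test for immunization. Neither has a significance level.
- **List of primary outcomes.** There is none. The protocol's Specific Aims number eight hypotheses (1a, 1b, 2a, 2b, 3a to 3d) without ranking them. Its End Points section lists project milestones: enrolment with data collection, and publication.

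**The concern.** The plan holds two rules for the same decision. The sample size paragraph claims control of the error rate over three primary outcomes, while the analysis paragraphs test each scale at two-sided 0.05. The 95% interval is not offered only as an estimate, because the text makes it the criterion for significance. Two analysts following different sentences of the same SAP could therefore reach opposite conclusions on self-efficacy whenever p lies between 0.0167 and 0.05.

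The missing list makes this worse. Self-efficacy and hospitalizations can be inferred from the power text, but the third primary outcome cannot. While it is unnamed, nothing in these documents prevents it from being chosen once the results are known.

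**Working it through.** **Inputs from Sample Size & Power:** 150 per group; 5 post-baseline visits; "We assumed a modest within-subject correlation of 0.50 between these repeated measures"; alpha 0.05 divided by 3; effect 0.33 SD; stated power 93%; no allowance for loss. Sidedness is not stated, but the 95% interval rule is two-sided.

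**1. The plan's own figure.**
- Variance of the mean of 5 equally correlated visits, in SD² units: (1 + 4 × 0.5)/5 = 0.60.
- SE of the group difference: √(2 × 0.60/150) = 0.0894 SD.
- Power = Φ(0.33/0.0894 − z), with 0.33/0.0894 = 3.69.

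| Level | z | Power |
|---|---|---|
| 0.0167 one-sided | 2.128 | 94.1% |
| 0.0167 two-sided | 2.394 | 90.2% |
| 0.05 two-sided | 1.960 | 95.8% |

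The stated 93% is close to the one-sided adjusted figure and lies between the two two-sided figures. It does not follow from the plain two-sided adjusted reading. The 99% for hospitalizations cannot be checked, because no SD or distribution is given.

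**2. Gap between the two rules for self-efficacy.**
- The per-test level is 0.05 against 0.0167, a factor of 3.
- The critical values are 1.960 and 2.394, a ratio of 1.221.
- The smallest observed difference in mean post-baseline score called significant is 1.960 × 0.0894 = 0.175 SD under the 95% rule, and 2.394 × 0.0894 = 0.214 SD at 0.0167.

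**3. Chance of at least one false positive over three primary outcomes.**

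| Levels used | Assumption | Result |
|---|---|---|
| All three at 0.05 | independent: 1 − 0.95³ | 14.3% |
| All three at 0.05 | correlation 0.3 (assumed) | 13.6% |
| All three at 0.05 | correlation 0.5 (assumed) | 12.5% |
| All three at 0.05 | upper bound: 3 × 0.05 | 15% |
| Two at 0.05, one at 0.0167 | independent: 1 − 0.95² × 0.9833 | 11.3% |
| One at 0.05, two at 0.0167 | independent: 1 − 0.95 × 0.9833² | 8.1% |
| All three at 0.0167 | independent: 1 − 0.9833³ | 4.9% |

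The mixed rows apply if a primary Aim 3 outcome is read as tested at the adjusted level.

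**4. Power for change from baseline, the planned measure.** This needs the correlation b between baseline and follow-up scores, which the documents do not give. With a score SD of 1, the variance is 0.60 + 1 − 2b. Two-sided power for 0.33 SD, 150 per group, no loss:

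| Assumed b | Variance | SE | Power at 0.05 | Power at 0.0167 |
|---|---|---|---|---|
| 0.3 | 1.00 | 0.1155 | 81.5% | 67.9% |
| 0.4 | 0.80 | 0.1033 | 89.2% | about 79% |
| 0.5 | 0.60 | 0.0894 | 95.8% | 90.2% |
| 0.6 | 0.40 | 0.0730 | 99.5% | 98.3% |

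If the stated SD and correlation describe the change scores themselves, the result is again 90.2% at 0.0167.

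**5. Candidates for the third outcome.** Eight hypotheses less self-efficacy and hospitalizations leaves six.

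**The case against.** The direct conflict is shown for one outcome only. Self-efficacy alone is both inferable as primary and governed by an explicit 95% rule. For Aim 1 and 2 scales that are not primary, a nominal 95% interval is acceptable. Silence on the Aim 3 level is a gap and could be filled by the adjusted level in the power paragraph. This stands, and it is why the family-wise error has a lower range of about 8% to 11%. Even that range exceeds 5%.

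The six candidates can also be narrowed. Calling hospitalizations the main infant outcome counts against the other Aim 3 hypotheses, which leaves stress, anxiety and depression. One primary outcome per aim would point to Aim 2. That is a fair inference, but the text does not state it, and Aim 2 itself has two hypotheses.

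One could also argue that Bonferroni in the power section implies Bonferroni in the analysis. It does not, because the analysis text states a different rule explicitly for both aims.

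Finally, a looser test gains power, so the sample size is not undermined, and only results with p between 0.0167 and 0.05 are affected. That is true, but those are the results on which the trial's main claim could turn.

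**Conclusion.** The concern holds and should be fixed before analysis. For self-efficacy the written rule tests at three times the level used to justify the sample size. Over three primary outcomes the false-positive risk is 12.5% to 14.3% if all are tested at 0.05 and the correlation is between 0 and 0.5, with a ceiling of 15%. It is about 8% to 11% for independent outcomes if Aim 3 outcomes are held to 0.0167. The plan's own statement implies no more than 5%. The correlations and the Aim 3 level are assumptions. The contradiction between the two rules, and the absence of a list of primary outcomes, are not. Neither depends on how the 93% was obtained.

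**What to change.** In both documents, before outcomes are compared by group:

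1. Name the three primary outcomes, in the End Points section and in Statistical Considerations.
2. Replace the 95% criterion for those outcomes with two-sided 0.0167. That means 98.33% intervals for outcomes analysed by GEE, and p < 0.0167 for any primary outcome analysed by rank-sum test. Holm is an acceptable alternative, with ordered p-values against 0.0167, 0.025 and 0.05.
3. Label every other outcome secondary, with nominal 95% intervals.
4. As a separate reporting point, state the sidedness and variance basis of the 93%, and restate power for the two-sided test used. Give the assumed baseline-to-follow-up correlation if the measure is change from baseline.

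**Cost.** The change is to wording, and N stays at 300 because the sample size text already claims the adjusted level. Primary intervals become about 22% wider. Two-sided power for 0.33 SD falls from 95.8% to 90.2% for the mean post-baseline score. For change from baseline, it falls from 81.5% to 67.9% at an assumed correlation of 0.3, from 89.2% to about 79% at 0.4, and from 99.5% to 98.3% at 0.6. These figures assume no loss. With an assumed 20% loss (120 per group), power at 0.0167 is about 82% for the post-baseline mean and about 68% for change at a correlation of 0.4. The sponsor should see these figures when restating power.

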The evaluation of the Parent Navigation NICU to home program will use a randomized trial design. We will do so by recruiting a population of parents who have an infant in the Children's National NICU, half of whom will receive enhanced usual care by provision of a NICU care notebook and half of whom will receive the same enhanced care- including care notebook- plus Parent Navigation (intervention). All will be patients in the NICU who are discharged from the CNMC NICU. Group assignment will be by randomization, stratified by birth weight (≤ 1500 grams or >1500 grams). The design incorporates extensive measurement of baseline attributes to assess the comparability of intervention and enhanced control groups at inception.

We aim to enroll $n=300$ parents of infants receiving care in the Children's National NICU who are discharged from the CNMC NICU. CNMC has a Level IV NICU which receives a large number of complex cases. To allow for generalization of study findings to other NICUs and other centers, we will enroll all patients discharged from the CNMC NICU.

Study personnel will identify eligible NICU patients by reviewing NICU census data or through the use of the PowerTrials Prescreening function. PowerTrials is a HIPAA-compliant application that is integrated into the Children's National Cerner electronic medical records system (PowerChart). Study inclusion and exclusion criteria will be used to create a Prescreening Rule. A screening engine in PowerChart will compare the criteria to patient data within the medical records system, and a list of potential study subjects will be generated.

Research study staff will approach parents anticipating discharge within 1-2 weeks to invite their participation and, as appropriate, obtain informed consent. If parents of eligible patients are not available, we may contact a parent by phone to set up a time to discuss the study in person. We will obtain in person signatures of consent as appropriate before enrolling potential participants in the study. Recruitment will continue in this fashion until the required sample is enrolled.

Inclusion criteria include:

NICU patients discharged from the CNMC NICU. One parent participant per NICU patient will be identified and enrolled as the participant.

Exclusion criteria include:

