**GPS (Giving Parents Support): Parent Navigation After NICU Discharge**

**NCT02743472**

**Statistical Analysis Plan**

**Updated/approved by Children's National IRB: 2/15/17**

**PI: [name], MPH**

### **Statistical Considerations:**

We will conduct intent-to-treat analyses to assess effects of the PN intervention such that randomized families will be analyzed according to their assigned intervention group, regardless of departures from the randomized intervention. While it is possible that families may seek some type of parental support independently of the intervention, these potential effects may be evaluated in sensitivity analyses. Our analysis strategy will first compare baseline characteristics between the PN and control groups to evaluate the balance produced by randomization. It is expected that randomization with stratification on one key confounder of birth weight ( $\leq 1500$  grams or  $>1500$  grams) will result in a balanced distribution of factors between the PN and care resource groups on most, if not all factors. However, even with randomization some imbalance may occur on a few factors and it is important to identify such factors, as these are the ones that need to be controlled during analysis.

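### The plan is inconsistent about whether the Aim 2 anxiety and depression models contain the birth-weight stratum used in randomization

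*SAP*

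**What the plan says.** The Protocol, under Research Design and Methods, states: "Group assignment will be by randomization, stratified by birth weight", with a cut at 1500 g. The SAP, Statistical Considerations, describes this as "stratification on one key confounder of birth weight", so the plan itself presumes that birth weight is related to outcome.

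The rules for adjustment in the SAP are these:

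- **Aim 1 (self-efficacy, stress):** "The model will include covariates reflecting the randomization stratification variables, and other covariates only if imbalances are observed". The stratum is unconditional; only the other covariates depend on imbalance.
- **Aim 2 (anxiety by STAI, depression by CES-D):** "If necessary, the models will include covariates known to impact parental depression and anxiety (if different between the groups) and stratification variables". The sentence opens with a condition of necessity and gives no criterion for it.
- **Link from Aim 2 to Aim 1:** the adjusted mean difference is to be compared between "groups using GEE models as described above (Aim 1").
- **Depression inside the Aim 1 text:** "We will assess the overall change in scores for the self-efficacy and depression scales".
- **Decision rule for Aim 2:** "The difference will be considered to be statistically significant if the 95% CI around the difference fails to include 0".

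The Protocol's Statistical Considerations section has the same wording for both aims, so neither document corrects the other.

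**The concern.** A factor used to stratify randomization is part of the design, and the analysis should normally carry it. Here one aim requires it and the next makes it optional on a criterion that nobody has written down. For depression there are two rules: always adjusted by the Aim 1 text, conditionally adjusted by the Aim 2 text. Two competent analysts could fit different models for Hypotheses 2a and 2b and both claim to follow the SAP. The choice could also be made after the data are seen.

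The numerical stake is precision. When allocation is balanced within strata, the difference between arms is already free of the between-stratum variation. A model without the stratum still counts that variation as residual error. Its standard error is then larger than the true sampling error, the 95% interval is too wide, and the test rejects less often than 5% under the null.

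**Working it through.** **1. The plan's own figure.** No power or interval width is given for Aim 2. The nearest figure is 93% power for Aim 1: 0.33 SD, 150 per arm, five post-baseline measures, within-subject correlation 0.50, alpha 0.05/3 (SAP, Sample Size & Power).

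- SD of a parent's mean over five measures: sqrt((1 + 4 × 0.5)/5) = sqrt(0.6) = 0.775. With correlation 0.5, the mean change from baseline has the same SD.
- SE of the difference: 0.775 × sqrt(2/150) = 0.0894. Effect/SE = 0.33/0.0894 = 3.69.
- Power at 0.05/3: 90.2% two-sided, 94.1% one-sided. Two-sided 0.025 gives 92.6%.

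The stated 93% is therefore approached only with a one-sided test or a different alpha, and the plan does not state sidedness. Nothing below depends on this. For Aim 2 the stated rule is a 95% interval, that is, two-sided 0.05, where the same inputs give 95.8%. That applies to the STAI state scale, which has five post-baseline measures. The Protocol schedules the CES-D four times after baseline, which gives 95.1%.

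**2. Effect of omitting the stratum.** Let R² be the stratum's share of the variance in a parent's mean score. The documents give no R², so the values are assumed. With balance within strata:

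- interval inflation k = 1/sqrt(1 − R²)
- true type I error = 2 × (1 − Φ(1.96 × k))
- power for 0.33 SD at two-sided 0.05 = Φ(3.69 − 1.96 × k)

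| Assumed R² | Interval too wide by | Type I error | Power |
|---|---|---|---|
| 0 | 0% | 5.0% | 95.8% |
| 0.02 | 1.0% | 4.8% | 95.6% |
| 0.05 | 2.6% | 4.4% | 95.3% |
| 0.10 | 5.4% | 3.9% | 94.8% |

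**3. Check by simulation** (20,000 trials, 300 families, balanced within strata, robust SE, an assumed 30% in the lower stratum). Mean interval width without and with the stratum was 0.359 and 0.349 at R² = 0.05, and 0.368 and 0.349 at R² = 0.10. Type I error without the stratum was 4.7% and 4.0%. At R² = 0 the widths agreed (0.349). Direction and size match the formula.

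**4. What these R² values require.** If the strata differ by d within-stratum SDs of the mean score, and a share p lies in the lower stratum, then R² = p(1 − p)d²/(1 + p(1 − p)d²). For p from 0.2 to 0.5 (assumed; the documents give no share):

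- d = 0.2 to 0.5 gives R² from 0.0064 (p = 0.2, d = 0.2) to 0.0588 (p = 0.5, d = 0.5), and intervals 0.3% to 3.1% too wide.
- R² = 0.05 needs d of about 0.46 to 0.57.
- R² = 0.10 needs d of about 0.67 to 0.83.

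**The case against.** The strongest reply is that the plan already adjusts. Aim 2 adopts the Aim 1 GEE model, speaks of a covariate-adjusted difference, and the Aim 1 text that requires the stratum names depression. This has weight: it rules out reading the plan as a settled decision to omit the stratum. It does not remove the problem, because the Aim 2 sentence is the more specific one and attaches a condition that Aim 1 lacks. For anxiety, the general cross-reference is all there is to set against it.

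A reader might also infer that the stratum enters Aim 2 only if the arms differ on it, which stratified randomization would almost never allow. The sentence does not say that. The parenthesis about group differences follows the covariates known to affect depression and anxiety and closes before the stratification variables are mentioned. Only the opening condition reaches the stratum, and the plan does not define it as a test of imbalance.

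The reply on size also stands. The power assumption of 0.33 SD of a single score equals 0.33/0.775 = 0.43 SD of a parent's mean score. Even R² = 0.05 needs a difference between strata larger than that. The power loss is 0.5 point at R² = 0.05 and 1.0 point at R² = 0.10.

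Finally, it is tempting to apply the same rule to Aim 3. The planned rank-sum test and t-test take no covariates, and post-discharge visits and admissions have no baseline value. That would mean new methods, so it is not part of this point.

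**Conclusion.** The inconsistency is real and should be resolved before analysis. The better ground for acting is that the model for two hypotheses is not fixed in advance; the gain in interval width is secondary. If the stratum is left out, intervals are about 1% to 5% too wide for assumed R² of 0.02 to 0.10, and not at all if birth weight does not predict the score. The error is on the conservative side. A reader might suspect bias or false-positive findings from the omission itself; neither follows.

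The size rests on two assumptions that the documents do not settle: the stratum's R², and close balance within strata. Blocking within strata is not described. Without it the unadjusted test would be nearer its nominal 5%, but adjusting would still gain precision when birth weight predicts the score.

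**What to change.** In the Aim 2 paragraph of Statistical Considerations, in both the Protocol and the SAP, state: *All Aim 2 models will include the birth-weight stratum (≤1500 g, >1500 g) and the baseline value of the outcome score, regardless of observed balance.* Remove the *If necessary* condition from the stratum. Changing only the SAP would create a new conflict with the Protocol.

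The baseline score goes beyond the inconsistency itself, but it belongs in the same sentence: it fixes the model further and usually gains more precision than the stratum does. The stratum is known from randomization, and the Protocol collects the STAI state scale and the CES-D at baseline. The cost is one sentence in each document, with no new data and no change to the sample size. Leave Aim 3 as it is for this purpose.

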3) Depression/Anxiety Measure: Parent depressive symptoms will be assessed using the Center for Epidemiological Studies- Depression Scale (CES-D) short form. This 10-item self-report measures depressive affect, somatic symptoms, positive affect, and interpersonal relations. Items are rated on a 4-point Likert scale. CES-D has adequate test-retest reliability and correlates well with clinical ratings of depression severity. This will be administered at baseline, 1 month, 3 months, 6 months, and 12 months.

4) Social Support: Parental perceptions of social support will be measured with the Multidimensional Scale of Perceived Social Support (MSPSS). This 12-item self-report scale includes respondents' support from family, friends, and significant other. The MSPSS has good internal and test-retest reliability and adequate construct validity. This will be assessed at baseline and 1 week, 3 months, 6 months, and 12 months post NICU discharge.

5) PSS: Parental Stressor Scale: The Parental Stress Scale is a self-report scale that contains 18 items representing pleasure or positive themes of parenthood (emotional benefits, self-enrichment, personal development) and negative components (demands on resources, opportunity costs and restrictions). This will be assessed at baseline and 1 week, 1 month, 3 months, 6 months, and 12 months post NICU discharge.

6) Parental NICU stress scale. PSS:NICU, a PROMIS measure. Will be administered at baseline only- 46 items.

7) Functional Status Scale is a measure of function in 6 areas: mental status, sensory, communication, motor function, feeding, and respiratory. The FSS will be performed at baseline and at 12 months, along with the developmental evaluation.

8) Perceived Stress Scale (Sheldon Cohen, 10 items) is a measure of the perception of stress. It will be performed at baseline and at 1 week, 1 month, 3 months, 6 months and 12 months after discharge.

Complete contact information will be collected at baseline and updated at each time point, including mobile numbers and contact information for someone who will know the whereabouts of the participant and be able to assist in locating them as needed.

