- Developmental testing between 12-15 months of age (or around 1 year corrected age if born prematurely). We will share the results with parents and pediatrician upon participant's request. Scores for five developmental domains (cognitive, language, motor, social-emotional and adaptive/behavioral) and the composite score for the Bayley Scales for Infant and Toddler Development TM, Third Edition (Bayley-III)(Pearson Educational) will be compared. Patients will be assessed in Developmental Clinic by [name] and her team. At the end of the assessment parents will be provided with immediate feedback and suggestions for ways to help the baby at home. A brief letter is sent to the pediatrician with copy to the family (and medical record). The full time for the assessment is about an hour. The parent is present, and the baby sits on parent's lap. [name] staff will set up the appointment when they are enrolled in the study and then have the study coordinator help with reminders. Parents can change the day/time to make it suit their own schedule. If needed, we will provide testing on Saturday to accommodate parents' schedules and to reduce burden.

If a participant has already had the Bayley-III administered at CNMC within the participant's designated study window, the data will be used, and family will qualify for a gift card.

Additionally, infant's medical records will be reviewed at baseline and at 12 months. See Data collection sheet in Documents section.

Description of Intervention:

Care notebook: All participants will be provided with a care notebook designed specifically for this study. It is an enhanced version of the resource notebook developed for use by the current parent navigators at CNMC, and is used to organize the care of medically complex children. The version of the care notebook in this study includes information important for NICU graduates, including available community resources, guidance on advocating for a child with special needs, healthcare providers and educational systems, and has sections where the parent or a healthcare provider can include information important for the child's care (e.g., medications, appointment calendar, care plans, seizure logs, therapy goals, dietary schedules).

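### The tests named for Aim 3 include neither covariates nor the birth-weight stratum, so the plan's rule on imbalanced factors cannot be carried out with them, and the Bayley-III has no analysis method

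*SAP*

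**What the plan says.** The opening paragraph of Statistical Considerations (same text in protocol and SAP) plans a baseline comparison of the two groups. Of any factors found imbalanced it says that "it is important to identify such factors, as these are the ones that need to be controlled during analysis". It does not limit this to particular aims. The same paragraph calls birth weight, the stratification factor, a key confounder.

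Aims 1 and 2 have models that can follow the rule. For Aim 1: "The model will include covariates reflecting the randomization stratification variables, and other covariates only if imbalances are observed". For Aim 2, if necessary, "the models will include covariates known to impact parental depression and anxiety (if different between the groups) and stratification variables".

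Aim 3 is different. Hospitalizations (called the main infant outcome under Sample Size & Power) and ED visits go to a "two-sample rank-sum test, which is appropriate for use with nonparametric data, such as the count data from this aim". For immunization: "This binary outcome will be contrasted using an unpaired t-test with unequal variances". No covariate, stratum or adjusted secondary model is mentioned for any of the three. The planned sensitivity analyses concern missing data and support obtained outside the study.

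The Bayley-III does not appear in the SAP. The protocol, under Infant health outcomes, lists "Scores for five developmental domains (cognitive, language, motor, social-emotional and adaptive/behavioral) and the composite score" and says of the instrument only "Third Edition (Bayley-III)(Pearson Educational) will be compared".

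On the FSS, the protocol's list of assessment tools (item 7) states: "The FSS will be performed at baseline and at 12 months, along with the developmental evaluation". It covers six functional areas. No analysis section mentions it.

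**The concern.** The plan commits to controlling imbalanced factors, then names tests for the infant outcomes that have no place for a covariate. If the arms differ by chance in infant severity, the analyst must either ignore the commitment for Hypotheses 3a to 3c or choose an adjusted method after seeing the data. Hypothesis 3d has no specified method to follow.

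Two baseline variables that could plausibly predict readmission, ED use and development are planned for collection: birth-weight stratum and FSS. Leaving them out gives up whatever precision they would bring. Stratifying the randomization and then omitting the stratum from the analysis also forgoes part of the benefit of stratifying.

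**Working it through.** **1. The rule against the methods**

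| Outcome | Method in SAP | Stratum or covariates |
|---|---|---|
| Parent scales (Aims 1, 2) | GEE | Yes, as quoted |
| Hospitalizations, ED visits | Two-sample rank-sum | None named |
| Immunization | Unequal-variance t-test | None named |
| Bayley-III | None | Not stated |

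**2. The plan's own power figure**

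Sample Size & Power gives 150 per group, a Bonferroni alpha of 0.05/3 = 0.0167, and 99% power for a difference of 1 in median hospitalizations. Sidedness is not stated; two-sided is assumed here. No SD, rate or count distribution is given, so the 99% cannot be reproduced, only inverted. Treating the difference as a shift of 1 under a normal approximation:

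SD = 1 / [(z for alpha + z for power) × √(2/150)] = 1 / [(2.394 + 2.326) × 0.1155] = about 1.83

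With the rank-sum efficiency factor 3/π applied to n, this is about 1.79. At larger SDs, power (normal approximation / rank-sum) is:
- SD 2: 97.4% / 96.7%
- SD 2.5: 85.8% / 83.9%
- SD 3: 68.9% / 66.5%

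**3. What adjustment would add**

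If baseline FSS has correlation rho with the outcome, adjustment multiplies the non-centrality by 1/√(1 − rho²). Rho is an assumption throughout.

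Power = Φ[(2.394 + z for unadjusted power)/√(1 − rho²) − 2.394]

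| Unadjusted power | rho 0.1 | rho 0.3 | rho 0.5 |
|---|---|---|---|
| 99% | 99.06% | 99.5% | 99.9% |
| 80% | 80.5% | 84.1% | 91.0% |
| Equivalent of 300 families, 300/(1 − rho²) | 303 | 330 | 400 |

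Example at 80% and rho 0.5: (2.394 + 0.842)/0.866 − 2.394 = 1.342, and Φ(1.342) = 91.0%.

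**4. Skewed counts**

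Simulated gamma-Poisson counts, 150 per arm, alpha 0.0167, 3,000 runs per setting, gamma shape 1, and log-rate slope b on a standard normal baseline score. Every input except n and alpha is assumed.

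| Control mean, rate ratio, b | Spearman | Rank-sum | Covariate-adjusted ranks |
|---|---|---|---|
| 1, 0.6, 0.4 | 0.21 | 52% | 54% |
| 1, 0.6, 0.8 | 0.38 | 39% | 45% |
| 2, 0.5, 0.8 | 0.41 | 79% | 87% |
| 2, 0.65, 1.2 | 0.54 | 24% | 34% |

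The gain is 2 to 10 points and grows with the correlation.

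**5. How likely is chance imbalance?**

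The standardized difference in one baseline factor has standard error √(2/150) = 0.1155. It exceeds 0.1 SD with probability about 39% and 0.2 SD with probability about 8%. For a continuous outcome, an imbalance of 0.2 SD moves the unadjusted contrast by rho × 0.2, which is 0.06 SD at rho 0.3 and 0.10 SD at rho 0.5. Conditional on that imbalance, the false-positive rate at nominal 5% is about 7% and 10% respectively. Averaged over all randomizations it stays at its nominal level.

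**6. Bayley-III**

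The plan gives no target effect. Borrowing 0.33 SD, which it states for self-efficacy, power is Φ[0.33 × √75/√(1 − R²) − 1.96] at two-sided 0.05: 81.5% at R² = 0, 85.4% at 0.10 and 91.0% at 0.25. This is illustrative only.

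**The case against.** The strongest reply is that nothing here makes the Aim 3 tests wrong. An unadjusted comparison in a randomized trial is valid, and its error rate already allows for chance imbalance. In a separate null simulation, both the rank-sum test and the covariate-adjusted rank test rejected 1.25% to 1.85% of the time against a nominal 1.67%. That stands: a reader might infer that the infant comparisons are biased, and the documents do not support that.

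The reply continues that the plan claims 99% power for hospitalizations, so adjustment can gain less than 1 point. That also stands if the 99% is right. But it rests on an unstated SD of no more than about 1.8, applies only to a median difference of 1, and says nothing about ED visits, immunization or the Bayley-III.

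Two other stronger readings are tempting. One is that the Bayley-III has been assigned a test without covariates. It has not: the SAP gives it no method, and the protocol's wording does not rule out adjustment. The fault there is an omitted analysis. The other is that the baseline FSS is never used. As a baseline attribute it falls under the planned comparison of the groups; it is only absent from the outcome analyses.

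It can also be said that item 7 does not state that the FSS precedes randomization. This is minor: the FSS is placed at baseline, and Consent and Recruitment puts the baseline surveys before randomization.

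**Conclusion.** The point holds as a gap between the plan's rule and its methods. The rank-sum test and the t-test, as named, cannot control an imbalanced factor and omit the randomization stratum; the baseline FSS is in no outcome analysis; the Bayley-III has no SAP method. These conclusions need no outside figure.

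The cost is in precision and in protection against chance imbalance; validity under randomization is not at stake. Its size cannot be derived from the documents. At two-sided alpha 0.0167 it is under 1 point if hospitalization power is truly 99%, and about 0.5 to 11 points for rho 0.1 to 0.5 if unadjusted power is 80%. A reader might infer a large, established loss of power; without an FSS-outcome correlation or a count distribution in the documents, that is not supported. The case for change is that adjustment is nearly free and removes a post hoc choice.

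**What to change.** In the Aim 3 text of both documents, pre-specify birth-weight stratum and baseline FSS total as covariates in every analysis, whether or not imbalance is seen:

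- **Hospitalizations and ED visits:** rank analysis of covariance, or a proportional-odds model, with arm, stratum and FSS. Keep the unadjusted rank-sum test as a sensitivity analysis.
- **Immunization:** a logistic or risk-difference model with the same terms.
- **Bayley-III:** add an analysis to the SAP, namely linear regression on arm, stratum and FSS, reporting the adjusted mean difference with its CI.

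State that any other factor found imbalanced may be added to these same models, which gives the general rule a route in Aim 3. State also that the baseline FSS is scored before randomization.

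The cost is SAP wording, one or two extra parameters per model, and a simple rule for a missing baseline FSS (for example a missing-value indicator). Both variables are already part of the planned baseline data, so no new collection is needed.
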